## COMT Inhibition as a Novel Treatment for Nicotine Addiction in Women

“wanting more of the drug” and “liking the drug”. This instrument allows rapid detection of nicotine effects, is adapted from a VAS (Soria et al. 1996), and has been used in our prior human laboratory studies with smokers (e.g., (DeVito *et al*, 2013)). This questionnaire will be administered at the *ad libitum* baseline based on the last cigarette they smoked that day (or one they smoke during allowable breaks) and post--abstinence final session based on the cigarette puffs smoked during the Smoking Choice Paradigm.

Center for Epidemiologic Studies Depression (CES-D) scale: The CES-D is a 20-item self-report measure of depressive symptoms (Radloff, 1977)) and will be administered at *ad libitum* baseline and final sessions.

State-Trait Anxiety Inventory (STAI): The STAI is a self-report questionnaire that includes two components: a 20-item component that measures ‘trait’ anxiety, which is expected to be stable over time, and a 20-item component that measures ‘state’ anxiety, which is expected to fluctuate across time (Kendall *et al*, 1976). Questions are rated on a 4 point scale from “almost never” to “almost always”. The ‘state’ component will be assessed at *ad libitum* baseline only while the ‘trait’ component will be included at *ad libitum* baseline and the post--abstinence final session.

Adverse Events Form: The SAFTEE form tracks adverse -effects of the medication and will be tracked at each visit and phone check-in once the medication (or placebo) has begun (Sofuoglu *et al*, 2001; Sofuoglu *et al*, 2005).

Timeline Follow-Back: Retrospective day-by-day self-report of past week smoking and substance use volumes(Robinson *et al*, 2014) will be carried out at the *ad libitum* baseline session and the one week follow-up.

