### B. Outcome Measures

COMT Inhibition as a Novel Treatment for Nicotine Addiction in Women

Table 1. Schedule of Assessments and Interventions	Time (min)	Screen	Ad Libitum Baseline	Brief Medication Visits Ivisit/day, 4 days	2 ½ day Abstinence End of Trial	1-week Follow-up
Screen & Baseline Measures & Smoking Behavior Measures						
Psychiatric and Medical Screen	35	X				
Demographics, Menstrual Cycle (MCAQ)	7		X			
Smoking History, Nicotine Dependence(FTND), urine cotinine dipstick	5	X				
Timeline Followback	5		X			X
Pill Administration, Abstinence Adherence and Physiological Measures						
Tolcapone or Placebo	2			X	X	
CO levels, Breathalyzer, urine cotinine	2	X	X	X	X	X
Urine toxicology	3	X	X	X (day 1)	X	
Urine pregnancy screen	3	X		X (day 1)	X	X
Vitals (HR, BP)	2	X	X	X	X	X
Blood Draws						
Genetics (rs4680)	3	X				
Labs for liver function	3	X			X	X
Nicotine, Cotinine, Hormones	3		X		X	
Self-report Measures of Withdrawal, Craving, Drug Effects, Mood and Impulsivity						
Withdrawal (MNWS); Smoking Urges(BQSU)	6		X	X	X	X
Subjective Nicotine Effect (DEQ)	2		X		X	
Adverse Drug Effects (AEF)	3			X	X	X
Depression (CES-D); Anxiety (STAI)	8		X		X	X
Affect (PANAS)	3		X	X	X	X
Impulsivity (BIS-II, BIS/BAS)	7		X			
Cognitive Tasks						
IQ	10	X				
Memory; Learning (digit span, HVLT)	25		X		X	
Sustained Attention (RVP, CPT)	10		X		X	
Cognitive Flexibility (CGT, SOC, Stroop))	10		X		X	
Laboratory Smoking Behavior						
Smoking Choice Paradigm	90				X	
TOTAL ESTIMATED TIME (hours):		1	1 ¾	1 ½ (20min/visit)	3	½

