Minnesota Nicotine Withdrawal Symptom Checklist (MNWS): At all sessions except screening, smokers will be asked to rate nicotine withdrawal symptoms (cigarette craving, irritability/anger, anxiety/tension, difficulty concentrating, restlessness, increased appetite, depressed mood, and insomnia) on a 100 mm scale, "not at all" to "extremely" (Hughes and Hatsukami, 1986).

Brief Questionnaire on Smoking Urges (BQSU): This 10-item scale reliably measures cigarette craving (Tiffany and Drobes, 1991) and will be administered at all sessions except screening.

Positive and Negative Affect Schedule (PANAS): The PANAS is a 20-item scale that assesses both negative and positive affective states (Watson *et al*, 1988). This scale is sensitive to the affective symptoms of tobacco withdrawal and predicts relapse to smoking (Kenford *et al*, 2002) and will be administered at all sessions except screening.

Premenstrual Assessment Form (PAF): Given their potential overlap with withdrawal symptoms (Allen *et al*, 1996; Allen *et al*, 1999; Carpenter *et al*, 2006), premenstrual symptoms will be assessed with the 10-item PAF (Halbreich *et al*, 1982) at all sessions except screening so they can be used as covariate in analyses focusing on withdrawal symptoms.

Drug Effects Questionnaire (DEQ): Smokers will rate 10 items that are related to nicotine effect on a 100 mm scale, "not at all" to "extremely." The items are feeling "stimulated", "high", "anxious", "sedated", "down", "good drug effects", "bad effects", "drug strength" as well as

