Abstinence Medication Maintenance Sessions (Medication Days 6-7): Beginning on the evening of Medication Day 5, subjects will be asked to refrain from smoking their cigarettes. They will be asked to attend one brief check-in session per day on Medication Days 6-7. Medication doses continue at 100mg TID during this phase. Smoking abstinence will be tracked with CO-levels, urine cotinine screens and self-report.

Post-2 ½ day Abstinence End of Trial Session (Medication Day 8): At the testing session, participants will have been abstinent from smoking for 2 ½ days or more (e.g., 8PM Medication Day 5 through 8AM Medication Day 8), and maintained on tolcapone (or placebo) for the previous week. Participants will take their final dose (100mg) on the morning of Medication Day 8 then complete the same self-report measures and cognitive tasks from the baseline *Ad libitum* Smoking session. Blood will be collected for assessment of nicotine and cotinine (as additional confirmation of abstinence), gonadal hormones and liver function tests (to screen for adverse effects of tolcapone).

Subjects will then complete the Smoking Choice Laboratory Procedure. As we have done in previous studies, participants will complete this paradigm in a designated, negative pressure room. After sample smoking (2 sec cigarette puffs separated by a 20 sec interval) to measure subjective responses to smoking following abstinence, participants exchange tokens for cigarette puffs (2 puffs) or money (\$0.75) every 9 minutes until 1.5 hours had elapsed (i.e., 9 min x 10

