Specific Aim 1: ANCOVAs will examine the effect of tolcapone on reducing a) withdrawal severity (MNWS); b) smoking urges (BQSU); and c) cognitive impairment (e.g., CPT) during abstinence vs. placebo. With 80% power, we can detect a large medication effect (f=.37). Specific Aim 2: ANCOVA will examine the effect of medication vs. placebo on laboratory smoking choices post-abstinence. With 81% power, we can detect a large effect (f=.40). Exploratory Aim 1: ANCOVAs will examine the effect of Met/_ genotype on reduced a) withdrawal severity (MNWS); b) smoking urges (BQSU); and c) cognitive impairment (e.g., CPT) during abstinence vs. Val/Val. With 80% power, we can detect a large genotype effect (f=.37). Exploratory Aim 2: ANCOVA will assess withdrawal and smoking post abstinence, using both medication and genotype as the independent variables and co-varying for baseline scores, to test for a medication by genotype interaction. With 81% power, we can detect a large effect (f=.40).

Exploratory Aim 3: Structural equation modeling will examine moderating effects of gonadal hormone levels on withdrawal severity and smoking behavior post-abstinence. The mediation effect size is unknown.

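### The STAI schedule runs against its own definitions: state anxiety is measured at baseline only and trait anxiety is repeated, and no other section clearly corrects it

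*Protocol*

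**What the plan says.** The STAI entry in Protocol section 5.B (Subjective/Questionnaires) describes two components. One is "a 20-item component that measures ‘trait’ anxiety, which is expected to be stable over time"; the other is "a 20-item component that measures ‘state’ anxiety, which is expected to fluctuate across time". The schedule follows: "The ‘state’ component will be assessed at *ad libitum* baseline only while the ‘trait’ component will be included at *ad libitum* baseline". The rest of that sentence adds the post-abstinence final session for the trait component. Neither component is assigned to the 1-week follow-up.

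Three other places bear on the schedule:

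- **Table 1** has one row for the CES-D and the STAI together ("Depression (CES-D); Anxiety (STAI"). It is marked at the *ad libitum* baseline, the end-of-trial session and the 1-week follow-up, and does not separate state from trait.
- **Section 5.E, End of Trial Session (Medication Day 8)** has participants "complete the same self-report measures and cognitive tasks from the baseline" session, with no exception for either STAI component.
- **Section 5.E, 1-Week Follow-up** refers to questionnaires on topics that include mood and smoking urges, but names no instrument.

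The SAP does not mention the STAI. Its Specific Aim 1 reads "ANCOVAs will examine the effect of tolcapone on reducing a) withdrawal severity (MNWS); b) smoking urges (BQSU", and then adds cognitive impairment.

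**The concern.** A measure expected to fluctuate is the one to repeat under drug and abstinence; a measure expected to be stable needs only a baseline reading. The STAI entry does the reverse. Randomisation follows the *ad libitum* baseline, so a state score taken only there precedes treatment in every participant. It can neither compare tolcapone with placebo nor show a change.

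Anxiety is part of the trial's rationale. The Background links anxiety symptoms to withdrawal and relapse in women, and links high COMT activity to anxiety in women. It reports higher anxiety ratings on placebo among women with high COMT activity, and predicts that COMT inhibition will ease negative mood. The SAP's power section also lists nicotine's anxiolytic effects among the genotype differences used as proxies for treatment effects. A Day 8 state score that was not collected cannot be obtained afterwards.

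**Working it through.** The plan states no figure to reproduce on this point. The check sets the schedule statements side by side and counts what each would collect.

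**Inputs**
- Items per component: 20 for state and 20 for trait (STAI entry).
- Planned completers: 60 (SAP, Power Analysis).
- Visits: as set out in each source.

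**Formulas**
- STAI items per participant = 20 × (state visits + trait visits).
- Post-randomisation state scores per participant = state visits after the *ad libitum* baseline.
- Total state scores = that number × 60, assuming all 60 completers attend each visit.

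| Reading | State visits | Trait visits | Items per participant | Post-randomisation state scores per participant | Over 60 completers |
|---|---|---|---|---|---|
| STAI entry as written | 1 | 2 | 20 × 3 = 60 | 0 | 0 × 60 = 0 |
| Day 8 procedure read literally | 2 | 2 | 20 × 4 = 80 | 1 | 1 × 60 = 60 |
| Table 1, both components at all three marks | 3 | 3 | 20 × 6 = 120 | 2 | 2 × 60 = 120 |
| STAI entry with the two words swapped | 2 | 1 | 20 × 3 = 60 | 1 | 1 × 60 = 60 |
| Swapped, plus state at follow-up | 3 | 1 | 20 × 4 = 80 | 2 | 2 × 60 = 120 |

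**Does another section settle it?**

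1. *Table 1.* It agrees with the STAI entry that some part of the STAI is given at baseline and end of trial, and adds a follow-up mark that the entry does not give. Because it names no component, it cannot correct the assignment.
2. *Day 8 procedure.* Read literally, it includes state anxiety on Day 8 and so contradicts the baseline-only instruction. It cannot be literal throughout, because BIS-11 and BIS/BAS are also baseline self-report scales and Table 1 gives them at baseline only. It is therefore no clear correction.
3. *Follow-up procedure.* It names no instrument, so it neither confirms nor removes the Table 1 mark.

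**Is the assignment consistent with the rest of the protocol?** No. The other scales described as measuring traits (BIS-11, BIS/BAS) are given at baseline only. Section 5.E has mood collected repeatedly because it is expected to vary with abstinence or medication. The STAI entry reverses that pattern.

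**The case against.** The strongest objection concerns importance. The STAI is in no aim, hypothesis or planned analysis, so no primary estimate, test or power figure changes. Anxiety in abstinence is still recorded at all sessions except screening. The MNWS items include "irritability/anger, anxiety/tension, difficulty concentrating, restlessness, increased appetite, depressed mood, and insomnia", and the protocol says of the PANAS: "This scale is sensitive to the affective symptoms of tobacco withdrawal". This stands and limits the severity. It does not remove the point: the MNWS offers one combined anxiety/tension item and the PANAS measures general affect, so neither replaces a multi-item, anxiety-specific state score. The DEQ item on feeling anxious concerns the response to smoking only.

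A second objection is that the conflict with the other sections is weaker than it looks. Table 1 differs only in the follow-up mark, which sits on a row shared with the CES-D and may not be meant for the STAI. If the Day 8 sentence is taken literally, state anxiety is collected and nothing is lost. Both readings are possible. But neither explains why the STAI entry would repeat the stable component, and staff working from the only component-specific instruction would not give the state form on Day 8.

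Third, a word swap is an inference. A deliberate choice to repeat the trait form cannot be excluded, and the swap drops a Day 8 trait score that the entry does schedule. That is fair, but a deliberate choice would need a stated reason and there is none. Finally, the counts above describe data collected, not bias, precision or power, and should be read only that way.

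**Conclusion.** The concern holds. The STAI entry contradicts its own definitions, and neither Table 1 nor the Day 8 procedure matches it or clearly corrects it. If the entry governs, there are 0 post-randomisation state-anxiety scores; the alternative readings give 1 or 2 per participant (60 or 120 over 60 completers). These totals assume full attendance, and the figure of 120 also assumes that Table 1 means both components at every marked visit, which no section states.

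The consequence is limited to a supporting measure. The Aim 1 and Aim 2 outcomes and the SAP's power figures are unaffected. What would be lost is the dedicated state-anxiety score on drug and in abstinence. The correction should be made because the loss is irrecoverable and avoiding it is nearly free. Confidence in the inconsistency is high; that it arose from transposed words is likely but not shown.

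**What to change.** In the STAI entry, swap the two words, so that the trait component is given at the *ad libitum* baseline only and the state component at baseline and the post-abstinence final session. If repeating the trait form was intended, give the reason and add the state form on Day 8.

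Then bring the other sections into line. Name the STAI component at each visit in Table 1, preferably on a row separate from the CES-D. Clarify in the Day 8 procedure which baseline self-report measures are repeated. State in the follow-up procedure whether the STAI is given and which component.

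No new planned test is needed. Any baseline-adjusted comparison of Day 8 state anxiety between groups should be labelled exploratory.

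The cost is one corrected sentence, a table label and clarifying phrases in the procedures. The swap leaves the burden at 60 items per participant. Keeping one 20-item component at follow-up, as the Table 1 mark already implies, makes it 60 + 20 = 80.

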## COMT Inhibition as a Novel Treatment for Nicotine Addiction in Women

Corp. Following oral administration, tolcapone reaches peak plasma levels within 1.5-2.0 hours and maximum inhibition of COMT activity in red blood cells is observed in 1-4 hours (Jorga, 1998; Jorga *et al*, 1998; Mannisto and Kaakkola, 1999).

Tolcapone's primary clinical use is in Parkinson's disease, as an adjunct to dopaminergic medications (e.g., levodopa) to optimize the balance and transitions between "on" and "off" states. In our study, smokers will take tolcapone at 100 mg dose three times a day (TID) for 7 days, and will receive a 100 mg dose on Day 8. Dose administration will be spaced by approximately 6 hours. Medication administration and oversight during the approximately one-week trial will be carefully monitored by our study nurse and physician.

*Justification for the tolcapone doses:* This dosing schedule is consistent with the manufacturer's recommended use of tolcapone. Previous recent studies with significant effects of the manipulation without problematic adverse drug effects began at 100mg TID for the first day then increased to 200mg TID (Apud *et al*, 2007; Grant *et al*, 2013), so our dosing is more conservative relative to these recent studies. Our dosing schedule is chosen to provide enough time to reach steady-state tolcapone levels (approximately 5 half-lives of tolcapone) prior to initiation of the abstinence period, then provide continued administration during the abstinence period.

Placebo: To maintain the double-blind, placebo pills will be designed to be visually identical to the tolcapone pills, and contain 25mg riboflavin to match the urine discoloration produced by tolcapone.

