## COMT Inhibition as a Novel Treatment for Nicotine Addiction in Women

(tolcapone) or placebo, in a double-blind fashion. Urn randomization will endeavor to balance medication and placebo groups for race, baseline smoking rate, and menstrual cycle phase. Although genotype will not be known for all subjects prior to randomization, in cases when it is known (e.g., genetics sample collected at baseline is processed prior to randomization) will be counterbalanced for genotype as much as possible.

Brief once-daily visits during the medication initiation (Medication Days 1-2) and abstinence periods (Medication Days 6-7) will serve four purposes: 1) administer pill in person and give take-home doses with instructions (100mg three times a day (TID); subjects will be asked to self-administer the take-home doses at approximately 6-hour intervals); 2) screen for adverse medication effects (Adverse Events Form; heart rate and blood pressure); 3) check for nicotine abstinence compliance (expired CO; urine cotinine; self-reported cigarettes per day); 4) collect self-report measures of withdrawal, smoking urges and mood, which are hypothesized to fluctuate with abstinence and/or medication.

Medication Initiation and Stabilization Phase (Medication Days 1-5): For the first five days of medication, subjects will be told they may smoke their cigarettes as much as they choose (*ad libitum*). They will be asked to attend one brief session per day on Medication Days 1-2. These first days will allow the participants to achieve medication optimal dosing and steady state levels prior to initiating the abstinence period. For Medication Days 3-5, the subjects will maintain the same dose and take the doses at home. During these days, they will have either in person/or phone check-in with a member of the research team to check for reported adverse effects. Brief questions about smoking (e.g., cigarettes per day) and whether they noticed changes in mood or smoking urges will also be asked. These phone check-in days are designed to maintain contact to continue monitoring for safety purposes, while reducing the burden on the participants. Subjects will have an emergency contact so they can access care if needed during this time.

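### No adverse-effects form is scheduled before the first dose and no rule defines a treatment-emergent symptom, so within-arm adverse-effect rates can include background complaints

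*Protocol*

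**What the plan says.** Protocol section 5.B (Outcome Measures), in the Adverse Events Form entry, states that "The SAFTEE form tracks adverse -effects of the medication" and that it "will be tracked at each visit and phone check-in once the medication (or placebo) has begun".

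In Table 1 of the same section, the row beginning "Adverse Drug Effects (AEF" takes 3 minutes. It is marked for the brief medication visits, the end-of-trial session and the 1-week follow-up. The screening and ad libitum baseline columns are blank.

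Section 5.E (Study Procedures) makes Day 1 one of the visits that include the form: "Brief once-daily visits during the medication initiation (Medication Days 1-2) and abstinence periods (Medication Days 6-7) will serve four purposes". Giving the pill is the first purpose listed. The second is to "screen for adverse medication effects (Adverse Events Form; heart rate and blood pressure".

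The protocol does not define a treatment-emergent event and has no attribution rule for ordinary events. Relatedness appears only in the individual and study stopping rules, for serious side effects. The SAP has no adverse-event analysis.

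**The concern.** The form's first scheduled use is at the visit where the first pill is taken. If that form and all later ones are tabulated as they stand, a headache or poor sleep that predates the study counts in the same column as one that began on tolcapone. The rate in each arm is then background plus drug effect, and nothing in the plan lets an analyst take the background out.

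What is at stake is how the safety data can be read. Women who already have a symptom cannot show it as new, and their reports add noise to both arms. Both effects make a real drug effect harder to see. In safety data, loss of sensitivity is the unwelcome direction.

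The gap also looks unintended. The withdrawal, urge, affect and premenstrual scales are given at every session except screening, and the depression and anxiety scales are given at baseline. Section 5.B includes the premenstrual form because those symptoms overlap with withdrawal and may need adjustment. The same reasoning applies to adverse effects, yet among the repeated symptom measures this form alone has no value from before the drug.

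**Working it through.** The plan states no figure on this point, so there is none to reproduce. The check has two parts.

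**1. What a Day 1 form can capture.**

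- Length of a brief visit (Table 1): about 20 minutes. Adding the row times gives 2 (pill) + 2 (CO and related tests) + 2 (vitals) + 6 (withdrawal and urges) + 3 (adverse effects) + 3 (affect) = 18 minutes. Day 1 adds 3 (toxicology) + 3 (pregnancy test), which makes 24 minutes.
- Pharmacology (section 5.D): "tolcapone reaches peak plasma levels within 1.5-2.0 hours and maximum inhibition of COMT activity in red blood cells is observed in 1-4 hours".
- Comparison: 20 to 24 minutes, against at least 60 minutes to maximum inhibition and at least 90 minutes to peak plasma level. A form completed during the visit falls before either stated peak, so most of what it picks up is likely to have been present already.

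These are times to peak, not to onset, so an early drug effect is unlikely but not excluded. Nor do the documents fix whether the form comes before or after the pill within the visit. The phrase about medication having begun and the order of the listed purposes both suggest after, but a list of purposes is not a sequence.

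**2. Illustration of the dilution.** All rates here are assumptions; the documents give none.

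Assumptions:
- 30 women per arm (60 completers split equally; the documents do not state the allocation ratio).
- A share *b* has a given symptom before dosing and goes on reporting it.
- Tolcapone causes it in *q* = 20% of women without it.
- No new onset on placebo.

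Formulas:
- Placebo rate = *b*
- Tolcapone rate *t* = *b* + (1 − *b*) × 0.20
- Difference = *t* − *b*
- Pre-existing share of tolcapone reports = *b* / *t*
- Power: two-sided 5% normal-approximation test of two proportions, Φ((*d* − 1.96 × SE0) / SE1), with *d* the difference, SE0 the pooled and SE1 the unpooled standard error

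| *b* | Background reports per arm (30*b*) | *t* | Difference | Pre-existing share | Power |
|---|---|---|---|---|---|
| 5% | 1.5 | 24% | 19 points | 21% | 55% |
| 10% | 3 | 28% | 18 points | 36% | 43% |
| 20% | 6 | 36% | 16 points | 56% | 28% |
| 30% | 9 | 44% | 14 points | 68% | 20% |

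Worked row: with *b* = 0.20, *t* = 0.20 + 0.80 × 0.20 = 0.36; difference 0.36 − 0.20 = 0.16; share 0.20 / 0.36 = 0.56.

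With no background the difference is the full 20 points. With a baseline record, the analysis can be limited to the 30(1 − *b*) women per arm without the symptom (28.5, 27, 24 or 21). In them the contrast is again 20% against 0%. The expected background is the same in both arms in every row, so its effect is dilution and not a shift toward either drug.

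**The case against.** The strongest case against the point has four parts.

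**Attribution.** A reader might infer that Day 1 symptoms are recorded as drug effects, or that they cannot be due to tolcapone. The documents support neither. They do not reproduce the form, say how an item is attributed or say whether onset is asked, and they give no time to onset of drug effect. This objection stands; the supportable claim is only that such symptoms can enter the rates.

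**Day 1 as a near-baseline.** If the Day 1 form mostly captures what was already there, it is close to a baseline, and later forms could be compared with it. This stands in part. Much of the information may exist, but the plan does not call it a baseline, does not place it before the dose and has no rule that uses it.

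**Existing references.** A reader might infer that the stopping rules have no pre-drug reference. They do. They concern serious side effects and name liver tests, which are taken at screening. Medical history, examination, ECG and vitals also precede dosing. The withdrawal checklist covers irritability, anxiety, concentration, restlessness, appetite, mood and insomnia, and is given before drug: "At all sessions except screening, smokers will be asked to rate nicotine withdrawal symptoms". The affect and premenstrual scales follow the same schedule. This stands, and the stopping rules form no part of the point.

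**No comparison is planned.** The aims and the SAP contain no adverse-event test, the trial was not sized for one, and the placebo arm balances background symptoms. This is true and limits the weight of the point. But balancing background symptoms does not remove them, and adverse-effect rates by arm would still be hard to read.

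**Conclusion.** The point holds as a minor gap in data collection. The form is not scheduled before medication, and no rule separates new or worsened symptoms from pre-existing ones. Within-arm rates can therefore be inflated by background complaints, and the between-arm contrast is weakened without being biased.

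The documents do not fix the size. In the illustration the contrast loses 1 to 6 of 20 points as the assumed background rises from 5% to 30%. This rests on equal arms of 30, a 20% drug effect, persistent background symptoms and no new onset on placebo. The documents do not support a count of women who would carry a spurious adverse effect, because they report no symptom prevalence in this population. No efficacy analysis is affected.

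**What to change.** State in three places in the protocol (the Adverse Events Form entry in section 5.B, the visit description in section 5.E, and Table 1) that the form is completed on Day 1 before the first dose and is labelled baseline. Keep recording every event from then on, including anything noticed later in the Day 1 visit. Add a line to the SAP that tabulates by arm, as treatment-emergent, those events that are new or worse than the baseline form.

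The cost is a wording change and one table. It is the same 3-minute form at the same visit, with no added visit or instrument, and no clinical rule changes.
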